11.2 Clinical Laboratory Variables

Descriptive statistics for clinical laboratory values (in SI units) and changes from baseline at each assessment time point as well as shift tables from baseline to each visit for quantitative variables will be presented by ethnic group and dose for the following clinical laboratory variables.

Hematology Hemoglobin, hematocrit, red blood cells (RBC), platelet count, white blood cell count – total and differential (WBC), total neutrophils (absolute), eosinophils (absolute), monocytes (absolute), basophils (absolute), lymphocytes (absolute).

Biochemistry Sodium, phosphorus, β -hCG^b, potassium, total protein, magnesium, glucose, total CO₂ (Bicarbonate), PTH^c, blood urea nitrogen, albumin, FSH^b, creatinine, aspartate transaminase (AST), calcium, alanine transaminase (ALT), chloride, gamma glutamyl transferase (GGT), thyroid stimulating hormone (TSH)^a, alkaline phosphatase (ALP), thyroxine (T₄ total)^a, total bilirubin, triiodothyronine (T₃)^a, uric acid.

CO₂=carbon dioxide; FSH=follicle stimulating hormone; T₃=triiodothyronine; T₄=thyroxine; TSH=thyroid stimulating hormone

^a See Table 1, Table 2, and Table 3.

^b Females only.

^c Parathyroid hormone at screening and Day -1 is for baseline eligibility use only and not for PK analysis.

Urinalysis pH, glucose, protein, blood, ketones, bilirubin, nitrites, leukocyte esterase, specific gravity.

Clinical laboratory test values are potentially clinically important (PCI) if they meet either the low or high PCI criteria listed in Table 4. The number and percentage of subjects with post-baseline PCI values will be tabulated by ethnic group and dose. The percentages will be calculated relative to the number of subjects with available assessments at that dose level. The numerator is the total number of subjects with at least 1 post-baseline PCI value at that dose level. A supportive listing of subjects with post-baseline PCI values will be provided including the subject number, ethnic group, dose, baseline, and post-baseline values.

Listings for serum and urinary clinical laboratory results will be produced for all patients in the Safety Analysis Set. Clinically potential important test results will be listed as well.

Table 4 Criteria for Potentially Clinically Important Laboratory Tests

Parameter	Classification (on CDRs)	Criteria
Biochemistry		
Sodium	HIGH	> 5 mmol/L (5 mEq/L) above ULN
	LOW	> 5 mmol/L (5 mEq/L) below LLN
Potassium	HIGH + INCREASE	Above ULN and increase of > 0.5 mmol/L (0.5 mEq/L) from baseline value
	LOW + DECREASE	Below LLN and decrease of > 0.5 mmol/L (0.5 mEq/L) from baseline value
Creatinine	HIGH + INCREASE	> 150 μ mol/L and increase > 30% from baseline value
BUN	HIGH	> 1.5 x ULN
Glucose (fasting)	HIGH	\geq 6.7 mmol/L
	LOW	\leq 4.2 mmol/L
Calcium	HIGH and INCREASE	Above ULN and Increase of \geq 0.25 mmol/L (1.0 mg/dL) from baseline value
	LOW and DECREASE	Below LLN and Decrease of \geq 0.25 mmol/L (1.0 mg/dL) from baseline value
Magnesium	HIGH and INCREASE	Above ULN and Increase of \geq 0.21 mmol/L (0.5 mg/dL) from baseline value
	LOW and DECREASE	Below LLN and Decrease of \geq 0.21 mmol/L (0.5 mg/dL) from baseline value
Phosphorus	HIGH	> 0.162 mmol/L (0.5 mg/dL) above ULN
	LOW	> 0.162 mmol/L (0.5 mg/dL) below LLN
Total protein	HIGH and INCREASE	Above ULN and Increase of \geq 20 g/L (2.0 g/dL) from baseline value
	LOW and DECREASE	Below LLN and Decrease of \geq 20 g/L (2.0 g/dL) from baseline value
Albumin	HIGH and INCREASE	Above ULN and Increase of \geq 10 g/L (1.0 g/dL) from baseline value
	LOW and DECREASE	Below LLN and Decrease of \geq 10 g/L (1.0 g/dL) from baseline value
Uric acid (with normal diet)	HIGH and INCREASE	Above ULN and Increase of > 0.119 mmol/L (2.0 mg/dL) from baseline value
	LOW and DECREASE	Above LLN and Decrease of > 0.119 mmol/L (2.0 mg/dL) from baseline value
ALT	HIGH	> 2 x ULN
AST	HIGH	> 2 x ULN
ALP	HIGH	> 1.5 x ULN
GGT	HIGH	> 1.5 x ULN
Total bilirubin	HIGH	> 1.5 x ULN
T4	HIGH	> 140.28 nmol/L
	LOW	< 57.92 nmol/L
T3	LOW	< 0.922 nmol/L

Table 4 Criteria for Potentially Clinically Important Laboratory Tests

Parameter	Classification (on CDRs)	Criteria
Biochemistry		
	HIGH	> 2.765 nmol/L
TSH	HIGH	>5.0 µU/L
	LOW	0.5 µU/L
Hematology		
RBC count	HIGH	>7.5 x10 ¹² /L
	LOW	<3 x10 ¹² /L
Hematocrit	LOW and DECREASE	≤0.6 x LLN and Decrease of ≥ 0.06 L/L (6.0%) from baseline value
	HIGH	>1.3 x ULN
Hemoglobin	LOW and DECREASE	< 100g/L (10g/dL) and Decrease of ≥ 20g/L (2.0 g/dL) from baseline value
	HIGH	>200 g/L (20g/dL)
WBC count	HIGH	>2xULN OR >16.0 x 10 ⁹ /L (16 x 10 ³ /µL)
	LOW	< 0.5xLLN OR < 3.0 x 10 ⁹ /L (3 x 10 ³ /µL)
Neutrophils	LOW	< 1.5 x 10 ⁹ /L (1.5 x 10 ³ µL) OR < 40%
	HIGH	> 6.2 x 10 ⁹ /L (6.2 x 10 ³ µL) OR > 70 %
Lymphocytes	HIGH	> 4.0 x 10 ⁹ /L (1.5 x 10 ³ µL) OR > 44 %
	LOW	< 0.8 x 10 ⁹ /L (0.8 x 10 ³ µL) OR < 22 %
Monocytes	HIGH	>11 %
Eosinophils	HIGH	> 0.5 x 10 ⁹ /L (> 500/µL) and > 10.0%
	LOW	NA
Basophils	HIGH	2%
	LOW	NA
Platelet count (thrombocytes)	HIGH	>1.5 x ULN OR > 500 x 10 ⁹ /L (100 x 10 ³ /µL)
	LOW	0.6 x LLN OR < 100 x 10 ⁹ /L (100 x 10 ³ /µL)
Urinalysis		
Glucose	HIGH	≥ 1+
Blood	HIGH	≥ 2+
Bilirubin		Normally not found
Protein	HIGH	≥ 2+
Nitrite		Normally not found
Ketones	HIGH	≥ 2+
Leukocyte Esterase		Negative

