2. STUDY OBJECTIVES AND PURPOSE

2.1 Rationale for the Study

Recombinant human PTH (rhPTH[1-84]) is approved for use in the United States (US) as an adjunct to calcium and vitamin D to control hypocalcemia in patients with hypoparathyroidism. As a once-daily SC injection for hypoparathyroidism, it has been shown to provide a 24-hour sustained increase in serum calcium. Administration of rhPTH(1-84) resulted in dose-related increases in total serum calcium levels, with maximum mean increases (approximately 0.125 to 0.175 mmol/L) observed 12 hours after dosing. Serum calcium levels did not return to baseline levels by 24 hours. This sustained increase may explain the reduction in the observed daily amounts of calcium and active vitamin D that were taken in the placebo-controlled trial.

Shire intends to develop rhPTH(1-84) for use in Japan. The Japanese regulatory agencies, Pharmaceuticals Medical Devices Agency (PMDA) and the Ministry of Health, Labor and Welfare (MHLW), require evidence that current data in non-Japanese subjects can be extrapolated to the Japanese population, since Japanese patients may require different doses of medication of some drug classes.

To satisfy the PMDA and MHLW requirements, sponsors will provide data to support doses for a later study in Japanese subjects. The present study to compare PK and PD profiles and safety and tolerability in Japanese and Non-Hispanic, Caucasian healthy volunteer subjects is designed for this reason. In addition, this study will also assess the PK dose-proportionality of rhPTH(1-84) using three, randomized, single, SC doses of 25 μ g, 50 μ g, and 100 μ g in healthy volunteers of Japanese descent.

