7.2.4.2 Shipment of Serum Pharmacodynamic Samples

All PD samples should be double-bagged to contain leaks and packed with a sufficient quantity of dry ice to ensure that they remain frozen for at least 72 hours to allow for delays in shipment. All applicable shipping regulations must be followed. Shipments should be scheduled so that no samples arrive on the weekend and should be shipped Monday-Wednesday only (do not ship on a local, regional or national holiday). Samples should be transported to ensure that they arrive at the bioanalytical laboratory between the hours of 9:00 AM and 4:00 PM. The recipient (inVentiv) and primary Shire contact must be notified by telephone or e-mail when the samples are shipped and they must be provided with the shipment tracking number.

Full directions for shipment of all PD samples, (along with the corresponding documentation) can be found in the laboratory manual provided under separate cover.

Pharmacodynamic samples will be stored nominally at -70° C (-94°F) prior to and after analysis at the bioanalytical labs until their disposal is authorized by Shire.

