^k There must be a minimum washout period of 72 hours (maximum 73 hours) from dose to dose for the volunteers of Japanese descent.

^l SAEs will be followed to resolution

Table 2 Detailed Schedule of Assessments (non-Hispanic, Caucasian Subjects)

Study Day	Day 1																	Day 2	
	Pre Dose 1	Pre Dose 2	0	10m	20m	30m	45m	1h	1.25h	1.5h	2h	2.5h	3h	4h	6h	8h	12h	16h	
Physical examination ^a																			X
Vital signs (BP, temperature and pulse) ^{a,b}		X ^e						X					X	X					X
TriPLICATE Electrocardiogram (12-lead) ^{a,c}		X ^e																	X
Biochemistry, hematology, and urinalysis ^a		X ^e																	X
Serum β-hCG Pregnancy test (females only) ^a																			X
Investigational drug administration			X																
Pharmacodynamic blood sampling ^d		X ^e												X	X	X			X
Anti-PTH antibody sampling		X ^e																	
Pharmacokinetic blood sampling	X ^f	X ^e		X	X	X	X	X	X	X	X	X	X	X	X	X	X	X	

BP=blood pressure; ECG=electrocardiogram; PK=pharmacokinetic, PTH=parathyroid hormone

^a In the event a subject is prematurely discontinued from the study or withdraws, every attempt should be made to complete these assessments.^b Vital signs will be obtained while subject is supine at times noted. Temperature only to be obtained at screening and at predose on Day 1.^c Electrocardiograms will be performed in triplicate at each timepoint.^d Pharmacodynamic blood sampling assessments will include serum calcium and phosphate and must be drawn before PK samples at the same timepoint.^e These assessments should be performed within 30 minutes prior to dose administration. The urine collection may be the first void of the day [providing that it is predose] but may be outside the 30 minute window if necessary.^f These assessments should be performed within 90 (±30) minutes prior to dose administration.

Table 3 Detailed Schedule of Assessments (Subjects of Japanese Descent)

Study Day	Days 1, 4 and 7																		Days 2, 5 and 8
	Pre-dose 1	Pre-dose 2	0	10m	20m	30m	45m	1h	1.25h	1.5h	2h	2.5h	3h	4h	6h	8h	12h	16h	
Hour (relative to dosing time)																			24h
Physical examination ^a																			X ^h
Vital signs (BP, temperature and pulse) ^{a,b}		X ^e						X					X		X				X
TriPLICATE Electrocardiogram (12-lead) ^{a,c}		X ^e																	X
Biochemistry, hematology, and urinalysis ^a		X ^e																	X
Serum β-hCG Pregnancy test (females only) ^a																			X ^h
Investigational drug administration			X																

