12.4.1 Original Pharmacodynamic Data

Blood samples for PD analysis will be collected at Predose 2 (within 30 min prior to dose administration), 4, 8, 12 and 24 hours after dose administration of rhPTH(1-84) for the determination of concentrations of serum calcium (uncorrected [total] and corrected for serum albumin levels), phosphate. Serum calcium will be corrected for serum albumin levels using the following equation:

Corrected calcium (mmol/L) = serum calcium (mmol/L) + 0.02 (40 - serum albumin (g/L))
(Parent X, 2009)

The serum calcium-phosphate product (using albumin-corrected calcium) will also be determined. This is calculated as serum calcium concentration (albumin-corrected) x serum phosphate concentration.

Individual original concentrations of serum total calcium, albumin-corrected calcium, phosphate and calcium-phosphate product will be listed and summarized with descriptive statistics (number, arithmetic mean, SD, CV%, median, minimum, maximum) by ethnic group, dose and time point.

Figures of individual original concentration-time profiles and mean (\pm SD) will be generated on linear scale for serum total calcium, albumin-corrected calcium, phosphate and calcium-phosphate product by ethnic group and dose. The mean plots will be created for the original concentrations of the above four PD markers by overlaying the mean values for each ethnic group and dose on the same figure.

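### The calcium PCI count rests on 24 h safety samples, although serum calcium is already measured at 4, 8 and 12 h and the protocol puts the peak mean rise at 12 h

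*SAP*

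**What the plan says.** **The PCI rule.** SAP 11.2 states: "Clinical laboratory test values are potentially clinically important (PCI) if they meet either the low or high PCI criteria listed in Table 4". The calcium HIGH criterion in SAP Table 4 has two conditions: a value above ULN, and an increase of at least "0.25 mmol/L (1.0 mg/dL) from baseline value". A LOW criterion mirrors it. On counting, the SAP says: "The number and percentage of subjects with post-baseline PCI values will be tabulated by ethnic group and dose", and then: "The numerator is the total number of subjects with at least 1 post-baseline PCI value at that dose level". The output is Table 4.6.6 (Biochemistry, Safety Analysis Set), with supporting Listing 8.1.2.

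**When safety calcium is drawn.** In SAP Tables 2 and 3 the row "Biochemistry, hematology, and urinalysis" is marked at Predose 2 and at 24 h, and nowhere between. The protocol's tables agree. Safety laboratory tests are repeated at follow-up, about 30 days after the last dose. SAP 11 reports follow-up under 100 µg whichever dose came last, and takes the last value before each dose as that dose's baseline. SAP 18.3 lets unscheduled post-baseline assessments count towards PCI.

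**When PD calcium is drawn.** SAP 12.4.1: "Blood samples for PD analysis will be collected at Predose 2 (within 30 min prior to dose administration), 4, 8, 12 and 24 hours". SAP 12.4 sends these values to descriptive tables, profile plots, AUC and Emax on the Pharmacodynamic Set, and SAP 20 adds Listings 5.7 to 5.9. None applies a PCI limit.

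**When calcium peaks.** Protocol 2.1 describes dose-related rises in serum calcium "with maximum mean increases (approximately 0.125 to 0.175 mmol/L) observed 12 hours after dosing", not back to baseline by 24 h.

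**The concern.** Hypercalcaemia is a named risk in protocol 1.3. Safety of each dose is a secondary objective, and protocol 9.9.2 plans a direct safety comparison of the two ethnic groups at 100 µg. The PCI table is the planned count of subjects with an important calcium change.

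As scheduled, that count looks at calcium 12 hours after the time at which the protocol's own background puts the largest mean rise. A low count in Table 4.6.6 could be read as little calcium change in either group when the likely peak was not counted. The 12 h measurements exist but are reported elsewhere, without a threshold.

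**Working it through.** **Step 1. Confirm the sampling times against the protocol's draw counts.** Protocol Table 4 (blood volumes) gives 5 biochemistry draws for a Caucasian subject and 9 for a Japanese subject, and 5 and 15 PD draws.

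- Biochemistry, Caucasian: screening, Day -1, Day 1 pre-dose, 24 h, follow-up = 5.
- Biochemistry, Japanese: screening, Day -1, Days 1, 2, 4, 5, 7 and 8, follow-up = 9.
- PD: pre-dose, 4, 8, 12, 24 h = 5 per dose; 3 × 5 = 15 for three doses.
- Volumes, Caucasian: 72 + 4 + 30 + 8.5 + 42.5 + 20 + 6 = 183 mL.
- Volumes, Japanese: 216 + 4 + 90 + 8.5 + 76.5 + 36 + 6 = 437 mL.

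All figures match. Biochemistry at 4, 8 and 12 h as well would need 5 + 3 = 8 and 9 + 9 = 18 draws, so it is not scheduled.

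**Step 2. Scheduled post-dose calcium times feeding the PCI count, per subject.**

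| Dose | As planned | With PD calcium added |
|---|---|---|
| 100 µg | 2 (24 h, follow-up) | 5 (4, 8, 12, 24 h, follow-up) |
| 25 µg, 50 µg | 1 (24 h) | 4 (4, 8, 12, 24 h) |

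Day 4 and Day 7 pre-dose samples are baselines for the next dose, so they do not add to the previous one. For Japanese subjects, follow-up comes after a last dose of 25 or 50 µg, so it says little about 100 µg.

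**Step 3. Illustrate the possible loss.** Only the rise condition can be illustrated, because the documents give no ULN. If the change from baseline is normal with mean m and standard deviation SD:

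P(rise ≥ 0.25) = 1 − Φ((0.25 − m) / SD); share missed = 1 − P(24 h) / P(12 h).

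From the documents: m at 12 h = 0.125 to 0.175 mmol/L. Assumed: SD 0.05 to 0.15 mmol/L, the same at both times, and 25% to 75% of the 12 h mean rise remaining at 24 h.

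Worked case: SD 0.10, m = 0.175 at 12 h, 75% remaining.

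- 12 h: (0.25 − 0.175) / 0.10 = 0.75, giving 22.7%.
- 24 h: m = 0.75 × 0.175 = 0.131; (0.25 − 0.131) / 0.10 = 1.19, giving 11.8%.
- Share missed: 1 − 11.8 / 22.7 = 48%.

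| SD | Mean rise at 12 h | P at 12 h | P at 24 h (25% to 75% remaining) | Share missed |
|---|---|---|---|---|
| 0.05 | 0.125 | 0.6% | about 0% to 0.1% | 86% to nearly all |
| 0.05 | 0.175 | 6.7% | about 0% to 0.9% | 87% to nearly all |
| 0.10 | 0.125 | 10.6% | 1.4% to 5.9% | 44% to 86% |
| 0.10 | 0.175 | 22.7% | 2.0% to 11.8% | 48% to 91% |
| 0.15 | 0.125 | 20.2% | 7.2% to 14.9% | 26% to 64% |
| 0.15 | 0.175 | 30.9% | 8.5% to 21.4% | 31% to 73% |

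The direction is built in, because a lower mean with the same SD must give a smaller tail. Only the spread of the last column is informative, and the assumptions set it.

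**Step 4. What holds without assumptions.** Within the PD series, the number of subjects with any PCI value over 4, 8, 12 and 24 h cannot be smaller than the number with one at 24 h alone.

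**The case against.** **The values are visible.** SAP 12.4 reports the maximum by ethnic group, dose and time point, individual profiles and Emax, and the values are listed. With 12 subjects per group, a rise of at least 0.25 mmol/L at 12 h would show in the baseline-adjusted maximum. This stands, so it would be wrong to say the excursions are hidden. But a maximum shows only that at least one subject rose that far. It does not say how many did, or whether the same subject was also above ULN.

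**The size is unknown.** A reader might infer that three quarters or more of excursions would be missed. That follows from some assumed values but not others. With mean rises of 0.125 at 12 h and 0.10 at 24 h, SD 0.08 gives 5.9% v 3.0% (about half missed) and SD 0.10 gives 10.6% v 6.7% (about 37% missed). These are not PCI rates either: the ULN condition is left out, and subjects enter with normal calcium. At any one time they are upper bounds, under the assumed distribution.

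**The background figures come from patients.** The 12 h peak is stated in a passage on hypoparathyroidism, and the 29 of 121 (24.0%) with hypercalcaemia in protocol 1.3 comes from hypoparathyroidism studies. Neither can be taken as an expected value for single doses in healthy adults. This stands. The peak time still gives a reason to look at 12 h.

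**Phosphate.** A reader might extend the point to phosphorus. The documents give no time for its extreme, so nothing shows that 24 h misses it.

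**Adverse event reporting may catch excursions.** PD samples are shipped "packed with a sufficient quantity of dry ice to ensure that they remain frozen for at least 72 hours" to a separate laboratory, and protocol 7.2.4 contains no step for returning calcium results to the investigator. That makes AE reporting an uncertain backstop. The documents do not say that investigators never see the results.

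**Nothing explicitly excludes PD calcium.** True. The exclusion follows from the separate sections, laboratories, analysis sets and outputs.

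**Conclusion.** The point holds as a gap in counting. Followed as written, the plan yields a calcium PCI count whose only scheduled sample within each dosing interval is at 24 h. At 25 and 50 µg that is the only scheduled post-dose sample. At 100 µg the other is follow-up, about 30 days after the last dose. The count can understate calcium excursions at each dose and in the ethnic safety comparison.

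The size cannot be derived from the documents. For the rise condition alone, the share missed at 24 h relative to 12 h runs from between a quarter and a third (26% to 31%, at SD 0.15 with 75% of the rise remaining) to nearly all. That range rests on assumed SDs, assumed 24 h means, normality, and a 12 h mean rise taken from a hypoparathyroidism context.

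The SAP calls its analyses exploratory (2.6) and the PD outputs show the raw values, so this is a cheap improvement and not a flaw that undermines the trial.

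**What to change.** In SAP 11.2, add a supplementary calcium count:

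- Apply the SAP Table 4 calcium criterion to PD serum total calcium at 4, 8, 12 and 24 h, with that dose's pre-dose PD value as baseline.
- Calculate the change from the original PD concentrations. SAP 12.4.2 sets negative baseline-adjusted values to zero, which would remove any fall and defeat the LOW criterion.
- Use the PD laboratory's reference limits. Protocol 7.2.2.5 promises reference ranges for the clinical laboratory; the PD sections mention none. If none can be obtained, report the change condition alone and say so.
- Report n (%) of subjects with any PCI value in 0 to 24 h, by ethnic group and dose, beside Table 4.6.6, and add these subjects to Listing 8.1.2.

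Phosphate may go in the same table for completeness.

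The cost is a few sentences of SAP text and one programmed table, from samples already planned, plus obtaining the PD laboratory's limits. The downside is that two laboratories' results appear in the safety section, so each count should name its source, and the reported rate may be less favourable.

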11. SAFETY ANALYSES

The safety analysis will be performed using the Safety Analysis Set. Safety variables include AEs and TEAEs, clinical laboratory variables, vital signs, and ECG variables. For clinical laboratory and vital sign variables, the last value collected before the dose administration will be used as baseline for all analyses of that safety variable in the respective dose interval. Thus there will be a different baseline for each dose for the Japanese subjects.

Follow-up visits will be summarized under the 100 μ g dose, regardless of which sequence the subject was randomized to, or which doses they had received.

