18.3 Repeated or Unscheduled Assessments of Safety Parameters

If a subject has repeated assessments before the start of investigational product, then the results from the final assessment made prior to the start of investigational product will be used as baseline. If post-baseline assessments are repeated, these will be captured as unscheduled visits, and the value recorded at the scheduled visit will be used for generating descriptive statistics. However, all post-baseline assessments will be used for PCI value determination and all assessments will be presented in the data listings.

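### SAP Table 4 defines a low uric acid as a value above the lower limit of normal, so the rule can never flag a low value

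*SAP*

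**What the plan says.** SAP 11.2 gives Table 4 operative force: "Clinical laboratory test values are potentially clinically important (PCI) if they meet either the low or high PCI criteria listed in Table 4". The resulting flags are counted by ethnic group and dose. For the numerator, "The numerator is the total number of subjects with at least 1 post-baseline PCI value at that dose level"; for the denominator, "The percentages will be calculated relative to the number of subjects with available assessments at that dose level". A supportive listing shows baseline and post-baseline values for the flagged subjects. SAP 18.3 widens the net to repeats, since "all post-baseline assessments will be used for PCI value determination".

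In Table 4 the uric-acid LOW and DECREASE row reads "Above LLN and Decrease of > 0.119 mmol/L (2.0 mg/dL) from baseline value". The HIGH and INCREASE row directly above it reads "Above ULN and Increase of > 0.119 mmol/L (2.0 mg/dL) from baseline value". A typical low-side row is potassium: "Below LLN and decrease of > 0.5 mmol/L (0.5 mEq/L) from baseline value".

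SAP 11.4 introduces Table 6 by calling an ECG variable PCI when its average reaches or passes the upper limits in that table. SAP 11.2 and 11.3 refer instead to low or high criteria.

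**The concern.** A value above LLN is not low, so the uric-acid criterion contradicts its own label. The row looks like the HIGH row with ULN changed to LLN and Increase changed to Decrease, but with Above left in place. SAP 17, which lists changes from the protocol, does not mention it, and no other section overrides it.

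Safety and tolerability are secondary objectives, and the PCI counts are one of the ways the plan reports them by ethnic group and dose. If the table is programmed as written, the uric-acid LOW entries in Table 4.6.6 and Listing 8.1.2 would consist of the wrong subjects.

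The ECG lead-in is a smaller conflict of the same kind. Read literally, it leaves out rows of Table 6 that are not upper limits.

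**Working it through.** **1. The threshold itself.** The row gives 0.119 mmol/L and 2.0 mg/dL as equivalents. With a molar mass of 168.11 g/mol for uric acid (a physical constant that is not in the documents, so an assumption here), 2.0 mg/dL = 20 mg/L, and 20 / 168.11 = 0.11897, or 0.119 mmol/L. The figure reproduces. The direction word is the only part of the row in conflict.

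**2. The decrease rows of Table 4 side by side.**

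| Analyte | Position required | Fall required |
|---|---|---|
| Potassium | below LLN | > 0.5 mmol/L |
| Calcium | below LLN | ≥ 0.25 mmol/L |
| Magnesium | below LLN | ≥ 0.21 mmol/L |
| Total protein | below LLN | ≥ 20 g/L |
| Albumin | below LLN | ≥ 10 g/L |
| **Uric acid** | **above LLN** | **> 0.119 mmol/L** |
| Hematocrit | ≤ 0.6 × LLN | ≥ 0.06 L/L |
| Hemoglobin | < 100 g/L | ≥ 20 g/L |

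Five rows say below LLN, two more use a low cut-off, and uric acid alone points upward.

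**3. What the rule does.** Above LLN and below LLN exclude each other, so the values flagged as written and the values the label describes have none in common, whatever the LLN. The documents give no uric-acid reference range. To illustrate, take an assumed range of 0.20 to 0.42 mmol/L:

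| Baseline → post-dose (mmol/L) | Fall | Post-dose position | As written | With Below |
|---|---|---|---|---|
| 0.42 → 0.29 | 0.13 | in range | flagged LOW | not flagged |
| 0.57 → 0.44 | 0.13 | above ULN | flagged LOW | not flagged |
| 0.31 → 0.18 | 0.13 | below LLN | not flagged | flagged LOW |
| 0.30 → 0.19 | 0.11 | below LLN | not flagged | not flagged |

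The same pattern appears with assumed ranges of 0.15 to 0.36 and 0.24 to 0.50 mmol/L. A false LOW flag needs a baseline above LLN + 0.119, which is 0.269, 0.319 and 0.359 mmol/L for assumed LLNs of 0.15, 0.20 and 0.24.

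**4. How many values the rule screens.** Visits come from SAP Table 1. SAP 11 allocates the follow-up visit: "Follow-up visits will be summarized under the 100" µg dose. Japanese Day 4 and Day 7 predose samples are left out because SAP 11 makes them the baseline for the next dose.

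- Caucasian 100 µg: 12 × 2 (Day 2, follow-up) = 24
- Japanese 100 µg: 12 × 2 (Day 2, follow-up) = 24
- Japanese 50 µg: 12 × 1 = 12
- Japanese 25 µg: 12 × 1 = 12
- Total: 24 + 24 + 12 + 12 = 72, plus any unscheduled repeats

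This counts values screened, not errors. With all 12 subjects of a cell assessed, one misclassified subject shifts the percentage by 1/12 = 8.3 points.

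**5. The ECG lead-in against Table 6.** A heart rate falling from 62 to 44 (a fall of 18) meets the low heart-rate row (≤ 45 with a fall above 15) but reaches no upper limit. The row for an abnormal overall reading has no limit at all. A man's QTc rising from 395 to 430 msec (an increase of 35) reaches the limit in the lead-in's sense, yet Table 6 requires more than 430. The table is coherent; the sentence introducing it does not fit it.

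**The case against.** The strongest reply is about weight. The intended meaning is plain from the label, the mirrored HIGH row and the sibling rows, and a competent programmer would probably apply it. The row concerns one flag for one analyte, SAP 2.6 calls the analyses exploratory, and no PCI count drives a decision. Table and listing specifications sit in a separate document (SAP 1) that is not available here and may already be right. The raw values also remain visible: Listing 8.1.2 shows baseline and post-baseline values, so a false flag could be noticed, and Listing 8.1.1 holds every result.

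Most of this stands, and it keeps the point small. It does not remove it. A silent correction in programming would be an undocumented departure from the SAP, and SAP 17 already records fixes as small as one footnote. One reassurance is weaker than it looks: shift Table 4.6.5 would show a missed low value only if its categories are low, normal and high, which SAP 11.2 does not state.

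It is also fair to say that uric acid is not the only questionable row. Lymphocytes HIGH pairs 4.0 × 10⁹/L with 1.5 × 10³, and platelets HIGH pairs 500 × 10⁹/L with 100 × 10³/µL. SAP 11.2 specifies SI units for the descriptive statistics, which softens those two, but the pairs still disagree. On the ECG side, Table 6 lists its low row explicitly, and SAP 11.3 applies the same low limits to pulse rate, so the practical risk from loose lead-in wording is slight.

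**Conclusion.** The uric-acid LOW criterion is wrong as written, and this follows from the text alone. No value below LLN can meet it, while in-range and high values can. The effect depends on the SAP being programmed literally and is confined to the descriptive uric-acid PCI counts and listing; PK and PD analyses are untouched. It bears on 72 planned values and 8.3 percentage points per misclassified subject, assuming 12 assessed per cell. The number of subjects miscounted cannot be estimated, because the documents give neither a reference range nor a variability for uric acid. The ECG lead-in also conflicts with its table, but only in wording. Both should be corrected before programming.

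**What to change.** In Table 4, change the first word of the uric-acid LOW and DECREASE criterion from Above to Below, leaving the 0.119 mmol/L (2.0 mg/dL) threshold as it is. In SAP 11.4, reword the lead-in so that an ECG variable is PCI when it meets the criteria listed in Table 6; this covers the low heart-rate row, the categorical row and the strict QTc limits together. While Table 4 is open, reconcile the lymphocyte and platelet HIGH unit pairs, and check that the separate output specifications carry the corrected rows.

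The two main changes cost one word and one phrase. They need no new data, no added output and no change to study conduct.
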